3 STUDY DESIGN

3.1 General Description

This is a phase II single-group pilot study. This trial is designed to evaluate efficacy and methylation. This study's overarching aim is to evaluate the systemic effects of BRBs in patients with MDS or MDS/MPN. Eighteen patients with MDS or MDS/MPN will be treated with 25 gm (2x/day) of BRB powder taken orally in 8 ounces of water. If the patient is unable to tolerate the taste of the BRB powder mixed in water, he or she may mix it with 8 ounces of milk, ice cream or a smoothie.

Anthocyanins in the blood will be measured within three hours prior to BRB administration, and two hours (+/- 30 minutes) after the first dose. Urine anthocyanins will be measured within three hours prior to BRB administration and three hours (+/-30 minutes) after the first BRB dose. Both of those time points were chosen based on previous studies demonstrating that the maximum concentrations of anthocyanins and ellagic acid in plasma occurred at one to two hours, and maximum quantities in urine appeared from zero to four hours. (20) Methylation status will be measured within three hours prior to BRB administration in cycles 1–4, 7, 10 and at the end of treatment visit.

Patients will receive oral BRBs while receiving their supportive care for a period of at least three cycles. At cycles 4 and 7, day 1, the patient will be assessed for response (Appendix 2) and toxicity. If the patient is tolerating BRBs well and is benefiting from therapy, he or she will continue treatment for a total maximum of 12 cycles. Tolerating well is defined as no grade 3 or 4 toxicity.

*Benefiting from therapy (for cycle 3 disease assessment) defined as CR, PR, HI, stable disease with no disease progression (see Appendix 2).

**Benefiting from therapy (for cycle 6 disease assessment) defined as CR, PR or HI (see Appendix 2).

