The research samples will be batched and any leftover blood/urine will be banked for future research. The research samples will be processed and banked at [name] lab at the R4655 TBRC, Medical College of Wisconsin, [name].

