10 STATISTICAL CONSIDERATIONS

Methods for berry components (ellagic acid and anthocyanins)

A descriptive analysis will be performed for ellagic acid and anthocyanin data. Means, medians and confidence intervals will be calculated for all absolute and relative differences.

Methods for analysis of methylation changes

The primary analysis will consist of six mixed effect models with a random effect for patient, and 4 pairwise comparison of baseline methylation to each treatment times. A Bonferroni correction for 24 total comparisons will be applied to maintain a 5% experimentwise error rate. The primary outcome will be analyzed as the relative methylation rate (difference/baseline). Absolute methylation will also be analyzed, if appropriate for this data. Missing data will be assumed to be missing at random (MAR). Patients with partial data before six6 cycles, e.g., from their visits at cycle 2 or 3, will be included in the analysis.

Power calculation

Strong changes in methylation levels have been observed in pilot data, with mean differences exceeding 20% difference, with standard deviations ranging from six to eight. This study calls for comparing the methylation differences from baseline to each treatment time points, and repeated over six different genes of interest, for a total of 24 comparisons. Based on a two-sided paired *t*-test with 5% type I error rate with Bonferroni adjustment for 24 comparisons, a standard deviation of 8.0 and methylation difference of 12%, a sample size of 16 will be sufficient for 95% power. To date, seven patients were enrolled to the trial and they all finished three cycles of BRB treatment. Based on the current compliance to the treatment protocol, no one dropped and no one was noncompliant. Therefore, we assume that there will be no more than 5% non-compliance to the treatment protocol. An addition of 5% will be recruited, so power can be maintained using nonparametric methods (Wilcoxon Signed-Rank test). Therefore, this brings the final sample required sample size to 18 patients to maintain the power of the study. *Toxicity monitoring plan (stopping rule)*

Severe toxicity is not expected with BRB. As a precaution for unexpected high toxicity, the trial enrolment will be pause and the protocol reviewed if a toxicity rate exceeding 15% is observed. The following table gives the stopping rule a Pocock-type boundary for 15% toxicity rate:

# enrolled	3	5	9	12	16	18
Pause if toxicities	3	4	5	6	7	8

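### Does the primary methylation model need rewriting because the plan is silent on the all-zero baseline row and on the unit of 12% and 8.0?

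*Combined protocol and SAP*

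**What the plan says.** Under the methylation heading of Section 10: "The primary analysis will consist of six mixed effect models with a random effect for patient", together with "4 pairwise comparison of baseline methylation to each treatment times", for 24 comparisons over six genes with a Bonferroni correction at 5% overall. The outcome for these models is the relative change from baseline: "The primary outcome will be analyzed as the relative methylation rate (difference/baseline". Absolute methylation is analysed too if it suits the data.

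The power paragraph restates the aim as a comparison of differences from baseline at each treatment time. It cites pilot data with "mean differences exceeding 20% difference, with standard deviations ranging from six to eight" and concludes, from a two-sided paired t-test, that with "a standard deviation of 8.0 and methylation difference of 12%, a sample size of 16 will be sufficient for 95% power". Two 5% allowances, the second so that a Wilcoxon signed-rank test keeps its power, bring the total to 18.

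Nothing in Section 10 or in the assay description (Section 9.3) says whether the baseline visit is a row in the relative-change model, or whether 12% and 8.0 are relative percent or percentage points.

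**The concern.** Comparing baseline with each later time is often coded with baseline as one level of a time factor. On the relative-change scale that level is 0 for everyone and has no variance. A random-intercept model with one residual variance would still give it the same variance as the other visits, so the standard error of each visit-minus-baseline contrast would generally be wrong. Two analysts could then report different p-values for the primary outcome from the same data, and the 5% overall error rate could be missed in either direction.

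The second worry is the sizing. The figure 8.0 has no unit, the 12% has no stated scale, and the plan analyses methylation on both the relative and the absolute scale. If the two figures did not belong together, the power claim would not hold.

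**Working it through.** **Inputs from Section 10.** Per-test error 0.05/24 = 0.00208; difference 12; SD 8.0; n = 16, inflated to 18; four post-baseline visits per gene; six genes. **Assumed, because the documents give no value:** ρ, varied from 0 to 0.9; equal SDs across visits; normal changes; complete data.

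**1. The plan's own figure.** For a two-sided paired t-test the standardised difference is 12/8.0 = 1.5. At n = 16 the noncentrality is 1.5 × √16 = 6.0 on 15 degrees of freedom.

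| n | Power |
|---|---|
| 15 | 95.7% |
| 16 | 97.3% |
| 18 | 99.1% |

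So 16 is sufficient for 95%. Inflation gives 16 × 1.05 × 1.05 = 17.6, which rounds up to 18. The figure reproduces.

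**2. Baseline row kept.** With k post-baseline visits of variance s² and correlation ρ, plus a row of zeros, the expected within-patient mean square is s²[k − (k − 1)ρ]/(k + 1). The model takes the contrast variance as 2/n times this; the true variance is s²/n. The ratio is 2[k − (k − 1)ρ]/(k + 1), which for k = 4 is 1.6 − 1.2ρ. At ρ = 0.5 it equals 1 for any k, so the neutral point does not depend on which of the scheduled samples make up the four visits.

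| ρ | Variance ratio | Per-test error, n = 16 | Per-test error, n = 18 |
|---|---|---|---|
| 0 | 1.60 | 0.0002 | 0.0002 |
| 0.25 | 1.30 | 0.0005 | 0.0005 |
| 0.5 | 1.00 | 0.0020 | 0.0022 |
| 0.75 | 0.70 | 0.0097 | 0.0099 |
| 0.9 | 0.52 | 0.028 | 0.028 |

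Errors are from 400,000 simulated balanced data sets per cell. A separate run at n = 16, treating the six genes as independent, gives an overall error of 1.7%, 4.2%, 12.0% and 27.5% at ρ = 0.3, 0.5, 0.7 and 0.9.

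**3. Baseline row left out.** When each visit's mean change is tested against 0, per-test error stays between 0.0020 and 0.0024 at every ρ. In the same separate run, overall error is 4.9%, 4.7%, 4.4% and 3.1%.

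**4. Which fit the plan points to.** The stated aim is to compare differences from baseline. The paired t-test and the signed-rank test both work on the within-patient change and test it against 0. The comparison wording in the model sentence fits absolute methylation, where baseline is a genuine measurement with its own variance. Nothing in the plan calls for a constant row in the relative-change model.

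**5. Unit.** Power in step 1 depends only on 12/8.0, so any common scale returns the same 16 and 18. The pilot sentence attaches its SDs of six to eight to mean differences, and the SD in a paired t-test is that of the differences. This identifies 8.0, the upper end of that range, as the SD of the change.

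**The case for a change.** The strongest case is that this is the primary analysis, that the text does not exclude the poor fit, and that ρ above 0.5 is believable. All changes share the one pre-dose sample of cycle 1 (Section 3.1: "Methylation status will be measured within three hours prior to BRB administration in cycles" 1–4, 7, 10 and at end of treatment). On the difference scale, equal and independent reading errors alone give ρ = 0.5, and lasting differences between patients in response would raise it. The wording would be cheap to settle: Section 10 says "To date, seven patients were enrolled to the trial and they all finished three cycles of BRB treatment", but Section 9.3 adds "The research samples will be batched", so the assay may not yet have been run.

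The algebra stands, and so does the point that the text leaves the baseline row open. What does not follow is harm from carrying out the plan. It needs an analyst to put a constant into an equal-variance model, against the change-based tests in the same section, and also a ρ well above 0.5 on the relative scale, for which the documents give no value. At ρ = 0.5 the error is nominal, and below it the fit is conservative.

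On the unit, it is true that if 8.0 were the SD of a single reading with no within-patient correlation, power at 16 would be 69%. The plan's own wording rules that reading out. It is also true that if 12 and 8.0 are percentage points, power for relative change would depend on a baseline level the documents do not give. That leaves the point unsized rather than showing the sample size wrong, and 12 is already well below the pilot differences of more than 20.

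**Conclusion.** No change to the plan is called for. The silence about the baseline row is a missing detail, and the rest of Section 10 leads an analyst to the sound choice: relative change at post-baseline visits, each visit mean tested against 0 at 0.05/24. Done that way, per-test error is 0.0020 to 0.0024 against 0.0021 whatever ρ is, under normal changes and balanced data.

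The alternative fit could put per-test error anywhere from about one tenth of nominal to about 13 times nominal (0.028/0.0021), but that range rests wholly on an assumed ρ and on a model the plan does not ask for. The sample size is unaffected: 16 and 18 reproduce with 12 and 8.0 on one common scale. The analyst can record the handling of the baseline row and the unit in the programming notes or the report; the primary scale, the 24 comparisons and the 18 patients stay as written.

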Complete blood count (CBC) with differential and platelet count	x	x	x	x	x	x	x
Pregnancy test (serum or urine) ⁵	х						
Serum chemistry panel ⁶	Х			Х			Х
Research serum for anthocyanin level ^{7, 15}		х					
Research blood methylation samples ^{8, 15}		x	x	х	х		х
Research urine samples9, 15		х					
Disease Response Assessment ¹²				Х			х
Transfusion history ¹³		х	x	X	Х	Х	х

¹ Screening procedures should occur within 28 days prior to Day 1. BRB treatment should start within 14 days of enrollment.

 2 A follow-up visit is required 30 days (+/- 4 days) from treatment discontinuation.

³ BRBs will be dispensed every cycle for a maximum of 12 cycles. BRB doses should be separated by at least six hours and the morning dose should be held when the methylation research samples are collected. Refer to appendix 5 for the drug diary.

⁴ Capture medications taken within 30 days of day 1 of BRB treatment.

⁵ For women of childbearing potential. This is defined as any woman whether or not they have undergone tubal ligation, that meets the following: has not undergone a hysterectomy or bilateral oophorectomy or has not been naturally postmenopausal for at least one year.

⁶ Including albumin, total protein, total bilirubin, ALT, AST, alkaline phosphatase, bicarbonate, sodium, potassium, chloride, creatinine, BUN, and glucose.

- ⁷ Blood will be collected within three hours prior to BRB administration and at two hours (+/- 30 minutes) after first dose of BRBs.
- ⁸ Study blood methylation samples will be collected within three hours prior to BRB administration.
- ⁹ Urine will be collected within three hours prior to BRB administration and at three hours (+/- 30 minutes) after first dose of BRBs.
- ¹⁰ If the patient is tolerating BRBs well and is benefiting from therapy, he or she will continue treatment for a total maximum of 12 cycles.
- ¹¹ All adverse events will be followed with appropriate medical management from the date the patient takes their first BRB dose until 30 days following the last dose of treatment. AEs are monitored continuously from the first dose of treatment to 30 days' post last dose
- ¹² Benefiting from therapy (cycle 4 disease assessment) defined as CR, PR, HI, Stable disease with no disease progression (see appendix 2). Benefiting from therapy (cycle 7 disease assessment) defined as CR, PR, or HI (see appendix 2).)
- ¹³ Capture transfusion history from eight weeks prior to day 1 of BRB treatment.
- ¹⁴ Refer to appendix 6.
- ¹⁵ Refer to appendix 4.

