In a study by Silverman et al., the median time to any response was two cycles (range 1–16). Overall, 91% of patients achieved best response by six cycles. Based on that, we will discontinue therapy for patients who do not achieve a response after six cycles. Response defined as CR, PR or HI (see appendix 2). (364) Our aim in this study is to evaluate the systemic effects of BRBs in patients with MDS or MDS/MPN.

Black raspberry dose

One of the most desirable features of a chemopreventive agent is little or no toxicity at concentrations producing chemopreventive efficacy. The toxicity of BRBs has been evaluated in rats fed a synthetic diet (AIN-76A diet) plus either 5% or 10% BRB powder by weight (w/w) for up to nine months. (19) These percentages of BRB powder in a rat diet would be equivalent to approximately 0.9 to 1.8 ounces (25.5 to 51 grams) of BRB powder in the daily human diet, as calculated on a body surface area basis. Histopathologic studies indicated that these BRB diets did not produce toxic effects in any major organs of the animals, and there were no significant differences in either body weight or food consumption between rats on either of the BRB-supplemented diets versus control rats on the AIN-76A-alone diet during the nine-month treatment. (19)

In humans, a phase I trial evaluated the safety and tolerability of BRB powder (45 g as a slurry in water daily for seven days) in healthy participants and results suggested that berries were well tolerated. In a subsequent pilot study of oral BRB powder (32 or 45g/day for six months) in Barrett's esophagus patients, BRBs were tolerated as well. (20) In that study, three of the 20 patients enrolled reported side effects that were likely related to BRBs. The reported side effects were epigastric pain, diarrhea and constipation; all were grade I.

Further, the daily dose of BRBs at 60 g (20 g x 3) was well tolerated in colon cancer patients

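### Missing methylation data are assumed MAR in a model without hematologic response, yet response decides who is sampled on treatment after C4D1, so the C7 and C10 contrasts may carry selection bias

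*Combined protocol and SAP*

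**What the plan says.** Section 10 (methods for analysis of methylation changes) specifies: "The primary analysis will consist of six mixed effect models with a random effect for patient", with "4 pairwise comparison of baseline methylation to each treatment times". It adds: "A Bonferroni correction for 24 total comparisons will be applied to maintain a 5% experimentwise error rate". On missing data it says "Missing data will be assumed to be missing at random (MAR" and keeps patients who have only early visits. It lists no response term, auxiliary variable or missing-data sensitivity analysis.

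Section 3.1 schedules methylation samples at cycles 1 to 4, 7 and 10 and at end of treatment, which makes six post-baseline times. The same section and footnote 12 of the Study Calendar make continuation depend on benefit. At C4D1, stable disease is enough. At C7D1 the rule is stricter: "Benefiting from therapy (cycle 7 disease assessment) defined as CR, PR, or HI". Section 1 agrees: "we will discontinue therapy for patients who do not achieve a response after six cycles". Section 3.1 also requires that treatment is tolerated, meaning no grade 3 or 4 toxicity.

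Section 3.3 sets the primary endpoint after three cycles, which is the C4D1 sample.

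**The concern.** A likelihood-based mixed model can ignore missingness that depends only on what the model conditions on. Here that is methylation at earlier visits. The design creates most of the missing C7 and C10 samples through a different variable, hematologic response. Suppose patients who respond also show larger falls in methylation than their earlier samples predict. The late visit means would then come from a favorable subset, and the contrast with baseline would move toward hypomethylation even with no average effect. A finding at C7 or C10 could not be separated from the effect of the continuation rule.

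**Working it through.** **1. The plan's own figure.** Section 10 states: "a standard deviation of 8.0 and methylation difference of 12%, a sample size of 16 will be sufficient for 95% power". The per-comparison level is 0.05/24 = 0.002083. For a two-sided paired t-test the noncentrality is (12/8) × √n, which is 6.0 at n = 16. Exact power is 97.4% at n = 16, and the smallest n giving 95% is 15 (95.7%). Enrolment is 16/0.95/0.95 = 17.7, rounded up to 18. The figure reproduces. It takes about 16 pairs for every contrast.

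**2. Which comparisons are exposed.** Of six post-baseline samples, three (C2, C3, C4) precede or coincide with the first continuation decision. With four contrasts per gene, at least 4 − 3 = 1 must be C7, C10 or end of treatment. Over six genes that is at least 6 of 24. Section 10 does not name the four. Its sentence on partial data refers to six cycles, which suggests C2, C3, C4 and C7. On that reading C10 lies outside the 24.

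**3. Who is sampled.**

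| Visit | Sample exists for |
|---|---|
| C2, C3, C4 | patients on treatment, before a continuation check acts |
| C7 | patients who passed the C4 check, stable disease included |
| C10 | patients who passed the C7 check: CR, PR or HI only |
| End of treatment | all who stop, about 30 days off treatment, at a time set by the stopping decision |

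The C7 sample is due at the same visit as the C7 assessment, so only the C4 check filters it.

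**4. Selection among sampled patients.** The documents give no response rates and no correlation between response and methylation, so both are assumed. Let p be the share of all patients sampled, ρ the correlation of response with the fall in methylation, and SD = 8 (section 10). With a true mean change of 0, the mean fall among those sampled is ρ × SD × φ(z)/p, where z is the upper-p normal cut-off.

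- p = 0.7: φ(z)/p = 0.497, so the fall is 1.19 points at ρ = 0.3 and 2.78 at ρ = 0.7.
- p = 0.2: φ(z)/p = 1.400, so the fall is 3.36 points at ρ = 0.3 and 7.84 at ρ = 0.7.

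**5. The stated model.** The mixed model recovers part of this through earlier samples. A random-intercept model was fitted by maximum likelihood to 20,000 simulated patients per scenario. Assumptions: true mean change 0; baseline SD 10; residual SD 3; patient-level change SD √(64 − 2 × 9) = 6.78, so that the change from baseline has SD 8 at C4, C7 and C10; change levelling off from C4; 60 to 80% continuing past C4; and 30 to 50% of those continuing past C7 (18 to 40% of all). Estimated change from baseline, in points:

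| ρ | C4, model | C7, model | C10, model | C7, sampled only | C10, sampled only |
|---|---|---|---|---|---|
| 0 | −0.06 to 0.01 | −0.10 to −0.02 | −0.16 to 0.05 | −0.10 to −0.02 | −0.25 to 0.06 |
| 0.3 | −0.07 to 0.03 | −0.59 to −0.27 | −1.15 to −0.77 | −1.30 to −0.67 | −2.88 to −1.89 |
| 0.5 | −0.02 to 0.09 | −0.98 to −0.44 | −1.80 to −1.20 | −2.18 to −1.10 | −4.78 to −3.15 |
| 0.7 | −0.08 to 0.08 | −1.44 to −0.66 | −2.87 to −1.90 | −3.15 to −1.57 | −7.11 to −4.75 |

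The row ρ = 0 is the control. It shows only simulation noise.

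**6. Dependence on the pattern of change.** With linear patient slopes (SD 1.0 to 1.5 points per cycle, 17 patients, 70% continuing past C4 and 30% past C7, ρ 0.3 to 0.7) the bias is 0 at C4, 0.8 to 2.5 at C7 and 2.7 to 8.8 at C10. These inputs are generous. Slopes alone give a change SD of 6 × 1.0 to 6 × 1.5 = 6 to 9 at C7 and 9 to 13.5 at C10, whereas section 10 cites six to eight. A further large-sample fit of the stated model gave 0, 0.2 to 1.5 and 0.4 to 5.7. Taken together: 0 at C4, 0.2 to 2.5 at C7, 0.4 to 8.8 at C10.

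**7. Numbers at C10.** If 18 to 40% of 18 patients reach C10, that is 3.2 to 7.2 patients. Paired-t power for the planned effect is 30% at n = 7 and 4% at n = 4.

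**The case against.** The strongest reply is that the trial's stated question is untouched. The endpoint is after three cycles, the C4D1 sample is due at the visit where the first decision is taken, and the bias there is 0. This stands, and it sets the limit of the point. Section 5.6 does allow stopping for progression at any time, but section 10 reports that all seven patients enrolled so far completed three cycles.

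Four further objections have force:

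- C7 is not restricted to responders, because the C4 check keeps stable disease. Only C10 is sampled in responders alone, and C10 may not be in the primary family.
- The direction of bias is not given by the documents. A reader might infer that the protocol expects responders to demethylate more. Section 2 lists methylation and hematologic response as separate objectives and posits no patient-level link.
- A reader might infer that MAR is false. Response is recorded, so MAR given all observed data may still hold. The gap is a conditioning variable left out of the model.
- A reader might infer a particular false-positive rate. In the linear-slope setting, rejection at nominal 0.002 was 1 to 4% at C7 and 6 to 43% at C10. A comparable run with zero correlation (assumed residual SD 3 to 5.6) already gave about 0.2 to 3% and 2 to 15%. Much of the excess is therefore random-intercept misfit, a separate matter, and no error rate is claimed here.

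The end-of-treatment samples are also a fair point, since stopped patients are still sampled. They do not fill the gap, because they are off treatment and their timing depends on the stopping decision.

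**Conclusion.** The point holds, with limited scope. An unqualified MAR statement is not adequate for visits after C4D1, because the variable that governs sampling is outside the model. At least 6 of the 24 primary comparisons are affected, or rest on end-of-treatment samples whose timing depends on the same decision. The effect is conditional: none if response and methylation change are uncorrelated, modest at C7 (about 0.2 to 2.5 points) and larger at C10 (0.4 to 8.8 points), against a planned difference of 12. The ranges rest wholly on assumed continuation shares, correlations and patterns of change. The upper ends need more spread in change than section 10 cites.

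The documents do not support the stronger reading that the primary result after three cycles is compromised, or that C7 and C10 are equally selected.

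**What to change.** Change section 10 as follows:

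- Rest the hypomethylation conclusion on the C4D1 contrast, with C2 and C3 as earlier time points, in line with section 3.3. Name the four contrasts. The divisor of 24 can stay; it is conservative for 6 × 3 = 18 comparisons through C4.
- Report C7 and C10 as supportive results among patients continuing treatment.
- Keep the MAR sentence but qualify it: for visits after C4D1, missingness is assumed random given earlier methylation and recorded response.
- Add one sensitivity analysis for C7 with the C4 response, already collected, as a covariate or auxiliary variable.
- State that C10 cannot be extended to all patients without extrapolation. A C7 response term does not help, because non-responders have no C10 sample. On a smaller scale the same holds at C7 for patients who progressed by C4: the sensitivity analysis reaches them only through the model's assumption about their later course.

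The cost is a few sentences and one extra analysis, with no new patients, visits or assays. The price is that the late contrasts become conditional and supportive. The continuation rule itself is not changed.

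### The 95% power in Section 10 is claimed for every treatment time but is supported only through cycle 4 day 1; later losses, including planned discontinuation, are not counted

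*Combined protocol and SAP*

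**What the plan says.** Section 10 (power calculation) describes the design as "comparing the methylation differences from baseline to each treatment time points", repeated over six genes, for 24 comparisons. The analysis paragraph of the same section specifies six mixed models and "4 pairwise comparison of baseline methylation to each treatment times". The power statement uses a two-sided paired t-test at a "5% type I error rate with Bonferroni adjustment for 24 comparisons" and concludes: "a standard deviation of 8.0 and methylation difference of 12%, a sample size of 16 will be sufficient for 95% power".

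The loss allowance follows: "we assume that there will be no more than 5% non-compliance to the treatment protocol". Its stated basis is that "seven patients were enrolled to the trial and they all finished three cycles of BRB treatment", with nobody dropping out. A further 5% is added so that power holds under the Wilcoxon signed-rank test, which gives 18.

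Methylation is sampled at baseline and on day 1 of C2, C3, C4, C7 and C10, and at end of treatment (Study Calendar, Appendix 4). Treatment continues past the C4 and C7 visits only with tolerability and benefit (Section 3.1 and Study Calendar footnotes). At the first decision stable disease counts as benefit. At the second it does not: "Benefiting from therapy (for cycle 6 disease assessment) defined as CR, PR or HI". The Background also says that patients without a response after six cycles will stop.

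**The concern.** The power claim covers all four times in the primary family, but the retention evidence ends at three cycles and comes from seven patients. The protocol itself plans to stop some patients after the C4 and C7 visits. That is scheduled discontinuation, so an allowance for non-compliance does not cover it, and it does not enter the sample size.

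At stake is whether a stated property of the primary analysis is true. If a late contrast is not significant, the plan's own text would describe it as a comparison with 95% power, whatever number of pairs remained.

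**Working it through.** **Inputs.** From Section 10: difference 12, SD 8.0, two-sided alpha 0.05/24, 16 pairs, 18 enrolled, 0 of 7 lost through three cycles. From the Study Calendar and Appendix 4: the sampling times. From Section 3.1 and the Study Calendar footnotes: the continuation rules.

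**1. The plan's figure.** Standardised difference = 12/8.0 = 1.5. Alpha per comparison = 0.05/24 = 0.00208. Power is the probability that |T| exceeds the two-sided critical t value, where T is noncentral t with n − 1 degrees of freedom and noncentrality 1.5√n. At n = 16 the noncentrality is 1.5 × 4 = 6.0 and the power is 97.3%. Fifteen pairs are enough for 95%. Inflation: 16 × 1.05 × 1.05 = 17.64, so 18. The stated sizes hold.

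| Complete pairs | Paired-t power per comparison |
|---|---|
| 18 | 99.1% |
| 16 | 97.3% |
| 15 | 95.7% |
| 14 | 93.1% |
| 12 | 83.7% |
| 11 | 76.3% |
| 10 | 66.7% |
| 9 | 55.2% |
| 7 | 29.6% |
| 5 | 9.6% |

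Simulated Wilcoxon power (normal data, exact critical values) is about 95.5% at 16 pairs and 93.9% at 15. So 18 enrolled can lose three patients and keep 95% by paired t, or two by Wilcoxon.

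**2. Which times are compared.** 24/6 = 4 times. Only three post-baseline samples (C2, C3, C4) fall at or before C4. At least one of the four must therefore be C7, C10 or end of treatment.

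**3. What 0 of 7 supports.** The exact one-sided 95% upper limit is 1 − 0.05^(1/7) = 34.8%; the two-sided limit is 1 − 0.025^(1/7) = 41.0%. At 34.8% loss, 18 × 0.652 = 11.7 pairs remain, so 11 to 12 pairs and 76% to 84% power. A true loss of 20% would still give 0 of 7 with probability 0.8^7 = 0.21, and 30% with probability 0.7^7 = 0.08.

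**4. Effect of the continuation rules, by visit.**
- C2, C3, C4: not thinned by them. The C4 sample falls at the visit where the first decision is made.
- C7: the sample is scheduled for the same visit as the second assessment, so only the C4 decision (progression or intolerance) and other dropout reduce the pairs. Power drops below 95% once more than three of 18 are lost (14 pairs, 93%; 12 pairs, 84%).
- C10: only patients with CR, PR or HI should remain. The documents give no response rate for black raspberries. As an illustration only, take the 30% to 50% that the Background reports for hypomethylating drugs: 18 × 0.30 = 5.4 and 18 × 0.50 = 9, so 5 to 9 pairs and about 10% to 55% power.
- End of treatment: scheduled for everyone at the follow-up visit after discontinuation, but it mixes treatment durations.

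**5. The Wilcoxon fallback.** Its smallest two-sided p-value is 2/2^n. At n = 9 this is 2/512 = 0.0039, above 0.00208. With nine or fewer pairs the test cannot reject at the plan's level.

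**The case against.** A reader might infer that no contrast after C4 can have 16 pairs unless nearly everyone benefits. The documents do not support that. Stable disease is enough to continue past C4, the response requirement at C7 cannot thin a sample taken at that visit, and the end-of-treatment sample carries no response condition. The response rule and the 10% figure belong to C10 alone.

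It is also fair to say that C10 may not be one of the four times. The sentence in Section 10 on partial data refers to six cycles, which hints at C2, C3, C4 and C7. That is a hint and not a definition, so the missing list of times is itself part of the defect.

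Further points stand in part:
- The primary objective is the change after three cycles, which is the period that the 7-of-7 completion covers. It is not undermined.
- The 34.8% is a limit, not an estimate of loss.
- The planning effect is conservative: pilot differences exceeded 20 with SDs of six to eight. At 20/8.0 = 2.5, nine pairs would give 98% power, but five still only 36%. The plan's claim is made at 12/8.0.
- The mixed models keep partial data under a missing-at-random assumption. That uses the data better but does not restore the pairs behind the 95% figure, and stopping depends on disease response.
- This is a pilot study, and no rule says how a null contrast will be read. Misreading is a risk, not a certainty.

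**Conclusion.** The point holds in limited form. The 95% figure is correct for 15 or more pairs and is reasonably supported through C4D1, where 18 enrolled leaves some slack. As a statement about every treatment time it is unsupported. At least one primary contrast falls after C4, the 5% allowance rests on 0 of 7 through three cycles, and planned discontinuation is left out.

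The size depends on which later time is meant. At C7 the shortfall may be nil or moderate, depending on losses that the documents do not project. At C10, if it is a primary contrast, power would be about 10% to 55% under the assumed 30% to 50% continuation. At end of treatment the number of pairs is not limited by the continuation rules; the difficulty there is mixed duration. All power figures assume the plan's difference of 12, SD of 8.0 and alpha of 0.05/24.

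**What to change.** Revise Section 10 as follows:
- Name the four comparison times.
- Limit the 95% power claim to contrasts through C4D1.
- For any later contrast, give a table of power by number of evaluable pairs, such as the one above.
- If C10 is included, treat it as descriptive or state its expected number of pairs and power. If end of treatment is included, say that it mixes treatment durations.
- Replace the assumed 5% ceiling with the observed 0 of 7 through three cycles and its exact upper limit (34.8% one-sided).

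No extra enrolment, visits or samples are needed, and the continuation rules need not change. The cost is a revision of the wording and a less favourable stated power at the later visits.
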